**Table 9-1 Schedule of reactogenicity assessments**

Day	Time	Performed by
0 a	Baseline: before vaccination	HVTN CRS clinician
	Early: 25-60 minutes after vaccination	HVTN CRS clinician
	Between early assessment and 11:59pm day 0	HVTN CRS clinician or participant
1-7 b	Between 12:00am and 11:59pm on the respective day	HVTN CRS clinician or participant

a Day of vaccination

b New or unresolved reactogenicity symptoms present on day 7 are followed until resolution

### 9.8.1 Assessment of systemic and local symptoms

Systemic symptoms include increased body temperature, malaise and/or fatigue, myalgia, headache, chills, arthralgia, and nausea. Local symptoms include pain and/or tenderness at the injection site. The daily maximum severity reached for each symptom during the assessment period is reported.

Body temperature is measured by oral or infrared thermometry. All temperatures must be measured by non-axillary thermometry. This includes temperatures taken in the clinic, as well as temperatures taken by participants during the reactogenicity period.

Temperature is reported in degrees Celsius. If temperature is measured in Fahrenheit, the conversion to Celsius should be documented in the participant's chart note. A measurement is taken once daily during the assessment period and should be repeated if participant is feeling feverish.

### **9.8.2 Assessment of injection site**

Typical injection site reactions are erythema/redness and induration/swelling. The maximum diameter for all injection site reactions is recorded.

All injection site reactions are monitored until resolution. Reactions with diameters greater than 5 cm are followed daily; otherwise, the frequency of follow-up is based on clinician judgment.

### **9.9 Visit windows and missed visits**

Visit windows are defined in HVTN 121 *Study Specific Procedures*. For a visit not performed within the window period, a Missed Visit form is completed. If the missed visit is one that required safety assessments or local safety labs, HVTN CRS staff should attempt to bring the participant in for an interim visit as soon as possible.

Procedures performed at an interim visit are usually toxicity/safety assessments (including local safety labs) and HIV testing. With the exception of HIV testing, these procedures are performed only if they were required at the missed visit or if clinically indicated. HIV testing may be performed as deemed appropriate by the study staff. Blood samples for immunogenicity assays are not typically collected at interim visits.

If a missed visit required vaccination, please refer to Section [7.3.2](#) and Section [7.3.3](#) for resolution.

### **9.10 Early termination visit**

In the event of early participant termination, site staff should consider if the following assessments are appropriate: a final physical examination, clinical laboratory tests (including CBC with differential, C3, C4, CH50, anti-dsDNA, urinalysis, spot urine protein:creatinine ratio, and chemistry panel), pregnancy testing, social impact assessment, and HIV test. For participants who have a confirmed diagnosis of HIV infection, see Section [9.12](#).

### **9.11 Pregnancy**

If a participant becomes pregnant during the course of the study, no more injections of study product will be given, but remaining visits and study procedures should be completed unless medically contraindicated or applicable regulations require termination from the study. If the participant terminates from the study prior to the pregnancy outcome, the site should make every effort to keep in touch with the participant in order to ascertain the pregnancy outcome. Pregnancies and pregnancy outcomes will be reported.

## 9.12 HIV infection during the study

If a participant becomes HIV-infected during the course of the study, no additional study product will be administered. Participants will be encouraged to continue scheduled study visits for up to 24 weeks following their last study product administration. Follow-up duration for participants diagnosed with HIV infection may be adjusted in consultation with the CRS investigator and the HVTN 121 PSRT (eg, to avoid interference with participant initiation of HIV treatment). At post-infection follow-up visits, only specimens required for protocol-specified safety laboratory tests, urinalysis, spot urine protein:creatinine ratio and pregnancy tests will be collected; in addition, some clinic procedures may be modified or discontinued (see [Appendix E](#) and [Appendix F](#)).

## 10 Laboratory procedures

### 10.1 HVTN CRS laboratory procedures

The HVTN 121 Site Lab Instructions and Study Specific Procedures provide further guidelines for operational issues concerning the clinical and processing laboratories. This document includes guidelines for general specimen collection, special considerations for phlebotomy, specimen labeling, whole blood processing, HIV screening/diagnostic testing, and general screening and safety testing.

Tube types for blood collection are specified in [Appendix E](#). For tests performed locally, the local lab may assign appropriate tube types.

In specific situations, the blood collection tubes may be redirected to another laboratory or may require study-specific processing techniques. In these cases, laboratory special instructions will be posted on the protocol-specific section of the HVTN website.

Of note, all assays described below are performed as research assays to evaluate the ability of the vaccine to induce immune responses in the context of the participants' genetic background, and are not approved for use in medical care. Results from these assays are not made available to participants or medical professionals to guide treatment decisions.

### 10.2 Total blood volume

Required blood volumes per visit are shown in [Appendix E](#). Not shown is any additional blood volume that would be required if a safety lab needs to be repeated, or if a serum pregnancy test needs to be performed. The additional blood volume would likely be minimal. The total blood volume drawn for each participant will not exceed 500 mL in any 56-day (8-week) period.

### 10.3 Primary immunogenicity timepoints

The primary immunogenicity timepoints in this study occur at baseline, 1 week and 2 weeks after the second AIDSVAX vaccination, and 1 week and 2 weeks after the third AIDSVAX vaccination.

Endpoint assays for humoral and cellular responses are performed on specimens collected from participants at the primary immunogenicity timepoints and may be performed at baseline. Depending on the initial results, assays for humoral and cellular responses may be performed on samples collected from participants at other timepoints; the schedule is shown in [Appendix E](#).

It is important to note that the same laboratories that will be running the neutralizing antibody assay and assays for the applicable secondary and exploratory endpoints in HVTN 121 were involved with the non-HVTN studies that will serve as controls (ie, RV328 and CHAVI 005). This will serve to minimize bias when comparing results across groups.

## **10.4 Endpoint assays: cellular**

### **10.4.1 Intracellular cytokine staining (ICS)**

Flow cytometry will be used to examine vaccine-specific CD4+ T-cell responses following stimulation of PBMCs with synthetic HIV peptides that span the proteins encoded by the vaccine. ICS parameters will include cytokines such as interferon gamma (IFN- $\gamma$ ), interleukin (IL)-2, and tumor necrosis factor (TNF)- $\alpha$ , and may include other cytokines (such as cytokines relevant to Th2 and Th17 responses) to identify T cells of specific functionality. Markers of cytotoxic potential (eg, granzyme B) and that identify circulating Tfh cells (eg, CXCR5 and PD-1) may also be included. Data will be reported as percentages of CD4+ T cells responding to a specific peptide pool. Additional cell surface markers, cytokines, or functional markers may also be analyzed.

### **10.4.2 T and B cell phenotyping**

Flow cytometry will be used to phenotype T and B cells in the peripheral blood. Peripheral follicular helper T (pTfh) cells and Treg cells may be characterized based on expression of CXCR5, PD-1, CD127, and CD25 on CD4+ T cells. Additional markers, comprising but not limited to indicators of activation or differentiation may also be included, such as CD21, CD27, CD38, and HLA-DR.

## **10.5 Endpoint assays: humoral**

### **10.5.1 Neutralizing antibody assay**

HIV-1–specific nAb assays will be performed on serum samples from study participants taken at the primary immunogenicity timepoints. The TZM-bl assay will test neutralization of the vaccine strains, a single highly neutralization-sensitive Tier 1 virus as a positive control and the global panel to assess Tier 2 neutralization [125,135]. Additional assays will be performed with viruses that are engineered to detect early precursors of bnAbs. Specimens from other timepoints may also be analyzed at the discretion of the HVTN Laboratory Program, which may be contingent on the results of the primary immunogenicity timepoints.

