Preliminary studies in mice including wild type and knock-in models of bnAbs have repeatedly demonstrated that antibodies of this type are controlled by tolerance mechanisms (9, 13-18). There are multiple murine models that have been used to examine the pathophysiology of SLE including therapeutic interventions (19), but such models do not have human B or T cell repertoires, suggesting that such models will be of limited use in evaluating vaccines that will be given to humans.

In support of the idea that SLE may be permissive for the development of bnAbs, an individual has been studied who developed SLE after becoming infected with

HIV-1. Although not protected from infection, over time this individual developed bnAbs and was able to control the virus without antiretroviral therapy (ART) (20). A monoclonal antibody (mAb), CH98, was isolated from blood B cells from this individual; this antibody broadly neutralized HIV-1 by binding to the HIV-1 gp120 Env CD4 binding site and displayed characteristics shared among HIV-1 bnAbs and antibodies commonly identified in autoimmune disease (long complementarity-determining region 3 loops and high mutation frequency). In particular, antibody CH98 is polyreactive (it reacts with more than 90% of 9,400 human host cellular antigens), and it specifically binds to double-strand DNA (dsDNA), a specificity that is commonly induced during SLE (21) and which was present in this patient whose plasma also contained anti-dsDNA autoantibodies (20).

While no human trial of HIV-1 vaccine candidates has elicited bnAbs, a number of results have suggested that an effective HIV-1 vaccine might be possible. The RV144 ALVAC-prime AIDSVAX-boost phase 2b vaccine efficacy trial, performed on HIV-uninfected individuals in Thailand, demonstrated 31% efficacy against acquisition of infection in low-risk subjects (22). The correlates of risk analysis showed that protection from infection correlated with antibodies directed against HIV-1 envelope protein (23). This has raised the possibility that with proper modification for enhanced vaccine efficacy, this vaccine could be made effective for general deployment.

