## 6 Statistical considerations

### 6.1 Accrual and sample size calculations

Recruitment for this single arm study will target enrolling 16 low-risk, HIV-uninfected adult participants, aged 18-50, who have also been diagnosed with SLE.

The primary purpose of this study is to explore the possibility that AIDS VAX® B/E may induce bnAbs in a population of participants diagnosed with SLE and to closely monitor participant safety. Since enrollment is concurrent with receiving the first study vaccination, all participants will provide some safety data. However, for immunogenicity analyses, it is possible that data may be missing for various reasons, such as participants terminating from the study early, problems in shipping specimens, low cell viability of processed peripheral blood mononuclear cells (PBMCs). Immunogenicity data from 17 phase 1 and 2 phase 2a HVTN vaccine trials, which began enrolling after June 2005 (data as of September 2014), indicate that 15% is a reasonable estimate for the rate of missing data at day 182. For this reason, the sample size calculations in Section 6.1.2 account for 15% of enrolled participants having missing data for the primary immunogenicity endpoint.

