#### 6.1.2 Sample size calculations for immunogenicity

The primary immunogenicity endpoint will be the production of bnAbs. This will be defined as a nAb geometric mean titer (GMT) greater than 100 against a standard HIV-1 pseudovirus panel. The sample size of 16 was selected such that if the true proportion of participants producing bnAbs in this population is at least 10 percent, we will have 81.5% probability of detecting bnAbs in at least one participant. If there is a dropout rate of 10% then we will still have a 77.1% probability of detecting bnAbs in at least one participant ([Table 6-2](#)).

**Table 6-2 Probability of detecting bnAbs in at least one participant, among different arm sizes, for different true event rates**

Number of Participants	True Population Percentage of SLE Participants Producing BnAbs			
	1%	5%	10%	25%
12	0.114	0.460	0.718	0.968
14	0.131	0.512	0.771	0.982
16	0.149	0.560	0.815	0.990
18	0.165	0.603	0.850	0.994

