### 6.3.4.2 Primary analyses of neutralization breadth and magnitude

The area-under-the-magnitude-breadth curve (AUC-MB) to a global panel of isolates (103) will be computed for each participant with evaluable neutralization data, as described in (104). Participant-level AUC-MB may also be computed for the historical controls, ideally based on the same global panel of isolates. The 95% CIs about the mean-differences in AUC-MBs between study cohorts will be reported. Regression models may be used to compare the AUC-MB between study cohorts, accounting for potential confounding factors such as age, gender, or other immune responses etc.

The analyses of magnitude-breadth described above are based on the endpoint area-under-the-curve, which is interpreted as the average  $\log_{10}$  IC50 to the set of isolates in the test panel. Use of this endpoint is maximally statistically powerful if one study cohort has greater magnitude and breadth than the comparator study cohort, but may miss an effect wherein one study cohort has greater magnitude and the comparator has greater breadth. Therefore, a secondary analysis may compare the distribution of magnitude-breadth curves among cohorts using the

test statistic  $\max|B_d^G|$  from Huang, et al (104), which is designed to detect general differences in magnitude-breadth curve distributions.

In addition, the geometric mean titers of Nab responses across a panel of isolates will be computed to determine the presence of bnAbs.

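### The protocol names no non-HIV-envelope control virus, and its bnAb rule (panel GMT above 100) requires neither Env specificity nor a rise from Day 0, so non-specific inhibition in lupus serum could be called a bnAb

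*Combined protocol and SAP*

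**What the plan says.** Section 10.5.1 gives the viruses for the TZM-bl assay: the vaccine strains, "a single highly neutralization-sensitive Tier 1 virus as a positive control and the global panel to assess Tier 2 neutralization". It adds: "Additional assays will be performed with viruses that are engineered to detect early precursors of bnAbs". Every virus described is an HIV-1 virus. No non-HIV envelope, and no other negative-control virus, is named anywhere in the protocol.

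Section 6.1.2 makes bnAb production the primary immunogenicity endpoint: "This will be defined as a nAb geometric mean titer (GMT) greater than 100 against a standard HIV-1 pseudovirus panel". Section 6.3.4.2 repeats the idea for the analysis: "geometric mean titers of Nab responses across a panel of isolates will be computed to determine the presence of bnAbs". Neither section sets a specificity condition, a background correction or a comparison with the participant's own Day 0 titre.

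The sample size rests on finding at least one such participant. At a true rate of 10% and n = 16, "we will have 81.5% probability of detecting bnAbs in at least one participant".

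The rationale in Sections 4.1 and 4.1.3 is that bnAbs share features with autoantibodies, polyreactivity among them. Of the bnAb isolated from a person with both lupus and HIV-1, Section 4.1 says "it reacts with more than 90% of 9,400 human host cellular antigens".

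Day 0 neutralization is part of primary endpoint 1 (Section 5.1), and footnote 6 of Appendix E commits to assays at Month 0. Section 10.3 lists baseline as a primary timepoint but then describes baseline testing as optional. In no version does the Day 0 result enter the bnAb rule.

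**The concern.** A neutralization titre records that a sample reduced infection; it does not record why. The Tier 1 virus shows that the assay can detect neutralization. It cannot show that inhibition acts through HIV Env, because it carries Env itself. A virus with a different envelope, run on the same serum, can separate the two.

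Breadth is the feature that non-specific inhibition would imitate. If a serum lowers infection by every panel virus at about the same titre c, the geometric mean over the panel is c, and any c above 100 satisfies the rule. The average log10 titre that AUC-MB represents would be raised too.

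Two features make this matter here. The population was chosen for altered tolerance and autoreactive antibodies, so activity against non-HIV targets is part of the hypothesis. And a single call carries weight: none of the 40 RV328 participants developed breadth (Section 4.3), and Section 4.1.3 plans mechanistic follow-up if any participant makes bnAbs. One false call could direct that work.

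**Working it through.** **Inputs from the protocol.** n = 16 (Section 6.1). The detection target is at least one participant with GMT above 100 (Section 6.1.2). Section 6.1.2 also says: "If there is a dropout rate of 10% then we will still have a 77.1% probability of detecting bnAbs". Section 6.1 instead says that "15% is a reasonable estimate for the rate of missing data at day 182".

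**Reproducing the plan's figures.** P(at least one) = 1 − (1 − p)^n.
- n = 16, p = 0.10: 1 − 0.90^16 = 0.8147 (plan: 81.5%).
- n = 14 (16 × 0.90 = 14.4, rounded down), p = 0.10: 1 − 0.90^14 = 0.7712 (plan: 77.1%).
- n = 16, p = 0.01 and 0.05: 0.1485 and 0.5599 (Table 6-2: 0.149 and 0.560).

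With 15% missing, 16 × 0.85 = 13.6, so n = 14 remains a reasonable second case; n = 13 would give 0.7458.

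**False calls.** Let f be the chance that one participant's serum reaches GMT above 100 through non-specific inhibition. Suppose no participant has a true bnAb and participants are independent. The chance of at least one false call is 1 − (1 − f)^n. The documents give no value for f, so the range below is an assumption. The last column also assumes that a control virus flags 90% of such sera, which leaves 0.1 × f.

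| f (assumed) | n = 16, rule as written | n = 14, rule as written | n = 16, control flags 90% |
|---|---|---|---|
| 0.5% | 7.7% | 6.8% | 0.8% |
| 1% | 14.9% | 13.1% | 1.6% |
| 2% | 27.6% | 24.6% | 3.2% |
| 5% | 56.0% | 51.2% | 7.7% |
| 10% | 81.5% | 77.1% | 14.9% |

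The first two result columns match Table 6-2 where the rates coincide because the formula is the same. That is not independent evidence about f. It does show that, when one positive is enough, a false rate f yields a positive finding as often as a true rate f.

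**What the unvaccinated samples can tell us about f.** Section 4.3 reports no HIV-1 neutralization in a tested subset of CHAVI 005. It gives neither the size of the subset nor how many of those tested had lupus. With 0 positives among m lupus samples, the one-sided 95% upper bound on f is 1 − 0.05^(1/m):
- m = 20 (assumed): 13.9%, so up to 90.9% for at least one false call in 16.
- m = 50 (assumed): 5.8%, so up to 61.7%.
- m = 125 (the whole lupus cohort, the largest possible): 2.4%, so up to 31.8%.

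These are upper limits, not estimates. They apply to people who had not been vaccinated.

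**The case against.** The strongest reply is that Section 10.5.1 is a short summary and that laboratory detail sits elsewhere. Section 14 lists a lab assay algorithm, Site Lab Instructions, Special Instructions and Study Specific Procedures, none of which is reproduced in the protocol. A reader might infer that the assay has no specificity control. The documents do not support that; they support only that the protocol does not name one or tie one to the bnAb call.

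A reader might also infer that lupus serum is known to inhibit non-specifically. It is not shown here. The antibody described in Section 4.1 is a monoclonal that is polyreactive and also a genuine bnAb against the CD4 binding site, so it illustrates shared features, not false neutralization. The only direct evidence, the CHAVI 005 subset, was negative. Samples from that cohort remain available for the same assays.

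Day 0 testing, binding antibody assays, epitope mapping (a secondary endpoint), and blocking and recombinant antibody work (Section 10.7) could all expose a false call. This stands in part. None of them is a condition of the call. Day 0 data cannot reveal activity that appears only after vaccination. Section 4.1.2 does cite a slight, non-significant autoantibody increase after influenza vaccination, but it reports no change in neutralization.

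Finally, a reader might take one positive among 16 as a formal success rule. It is not: Section 6.1.2 states a detection probability, Section 6.1 describes an exploratory purpose, and Section 6.3.4.2 puts AUC-MB comparisons first and the GMT in addition.

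**Conclusion.** The point holds as a gap in the written rule. Followed as written, the rule would label a serum a bnAb producer whether its inhibition acted through Env or not, and whether or not it was present before vaccination. RV328 does not close the gap, because its participants did not have lupus. CHAVI 005 closes it only in part, because its participants were unvaccinated and the number tested is not stated.

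The size of the risk is unknown. The figures of 14.9% to 56.0% are conditional on an assumed f of 1% to 5%, no true bnAbs and independence. They should not be read as the trial's false-positive rate, and f could be close to zero. What they show is that a detection target of one participant leaves little tolerance for an imperfectly specific call. This is worth correcting because the remedy is cheap and leaves the sample size and visits unchanged.

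**What to change.** 1. In Section 10.5.1, name one pseudovirus with a non-HIV envelope, run alongside the HIV panel on each participant's Day 0 and Day 182 serum. If the laboratory already does this, say so and cite the document.
2. In Sections 6.1.2 and 6.3.4.2, call a participant a bnAb producer only if the panel GMT exceeds 100, exceeds the control-virus titre by a fold that the laboratory fixes in advance, and rises from that participant's Day 0 value. State how a serum that fails only the control condition will be reported.
3. Make Day 0 neutralization testing mandatory in Section 10.3, in line with primary endpoint 1 and Appendix E.
4. Keep the uncorrected AUC-MB for comparison with RV328 and CHAVI 005. Correcting this cohort alone would break comparability. Report a control-corrected AUC-MB as a sensitivity analysis.
5. If a positive is confirmed with purified IgG, test that IgG against the control virus too. Purification alone does not remove polyreactive IgG.

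**Cost.** One extra virus on at most 16 × 2 = 32 sera, or about 16 + 14 = 30 with expected losses, plus a few sentences of text. Both blood draws are already in Appendix E. The downside is that a weak true responder with high background could be missed; reporting the uncorrected GMT beside the call keeps such a case visible.
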